#### **11.2.2.1. Cohort B1: Pediatric Subjects (<12 years) Who Are SARS-CoV-2 RT-qPCR Positive at Baseline**

Approximately up to a total of 250 pediatric subjects (<12 years) will be enrolled in this study. Of the 250 subjects, 10% (25/250) are expected to be enrolled in this cohort (ie, central lab RT-qPCR positive at baseline) for evaluating the drug concentration and exposure, and safety. No statistical hypothesis tests will be performed. The actual number of subjects in this cohort will depend on the actual percentage of subjects with a baseline positive RT-qPCR enrolled. No statistical hypothesis tests will be performed.

### **11.3. Analysis Sets**

#### **11.3.1. Efficacy Analysis Sets**

##### **Seronegative Modified Full Analysis Set (Seronegative mFAS-A) - Cohort A**

The seronegative modified full analysis set for cohort A (seronegative mFAS-A) includes all randomized subjects aged 12 years and older who are laboratory confirmed negative for SARS-CoV-2 (per central lab PCR test) and who test negative for antibodies for SARS-CoV-2 (per central lab serology testing) at baseline.

Subjects included in the administrative assessment analysis are excluded from the seronegative mFAS-A population.

Subjects will be analyzed based on the randomized treatment assignment. The seronegative mFAS-A population is the primary analysis population for the primary and secondary endpoints for cohort A of this study unless specified otherwise.

##### **Seronegative Modified Full Analysis Set (Seronegative mFAS-A1) - Cohort A1**

The seronegative modified full analysis set for cohort A1 (seronegative mFAS-A1) includes all randomized subjects aged less than 12 years who are laboratory confirmed negative for SARS-CoV-2 (per central lab PCR test) and who test negative for antibodies for SARS-CoV-2 (per central lab serology testing) at baseline.

Subjects will be analyzed based on the randomized treatment assignment. The efficacy endpoints for cohort A1 will be analyzed using the seronegative mFAS-A1 unless specified otherwise.

##### **Seronegative Modified Full Analysis Set (Seronegative mFAS-B) - Cohort B**

The seronegative modified full analysis set for cohort B (seronegative mFAS-B) includes all randomized subjects aged 12 years and older who have laboratory confirmed positive tests at

baseline for SARS-CoV-2 RT-qPCR and negative SARS-CoV-2 serology (both based on central lab testing) and are asymptomatic at baseline.

Subjects will be analyzed based on the randomized treatment assignment. The primary and secondary endpoints for cohort B will be analyzed using the seronegative mFAS-B unless otherwise specified.

#### **Seronegative Modified Full Analysis Set (Seronegative mFAS-B1) - Cohort B1**

The seronegative modified full analysis set for cohort B1 (seronegative mFAS-B1) includes all randomized subjects aged less than 12 years who have laboratory confirmed positive tests at baseline for SARS-CoV-2 RT-qPCR and negative SARS-CoV-2 serology (both based on central lab testing) and are asymptomatic at baseline. Subjects will be analyzed based on the randomized treatment assignment. The efficacy endpoints for cohort B1 will be analyzed using the seronegative mFAS-B1 unless otherwise specified.

#### **11.3.2. Safety Analysis Set**

The safety analysis set (SAF) includes all randomized subjects who received at least 1 dose or part of a dose of study drug. Subjects in the SAF will be analyzed based on the treatment received (as treated). In general, safety will be evaluated by study cohort: SAF-A (cohort A), SAF-B (cohort B), SAF-A1 (cohort A1), and SAF-B1 (cohort B1). However, injection site reactions will also be based on all cohorts combined.

#### **11.3.3. Pharmacokinetic Analysis Set**

The PK analysis population includes all subjects who received any study drug and who had at least 1 non-missing drug concentration measurement following study drug administration. Subjects will be analyzed based on actual treatment received.

#### **11.3.4. Immunogenicity Analysis Sets**

The ADA analysis set (AAS) includes all subjects who received study drug and had at least 1 non-missing ADA result after study drug administration. Subjects will be analyzed based on the actual treatment received.

#### **11.3.5. Neutralizing Antibody Analysis Set**

The NAb analysis set (NAS) includes all subjects who received any study drug and who are either negative in the ADA assay or positive for ADA with at least one non-missing result in the NAb assay after first dose of the study drug. Subjects who are ADA negative are set to negative in the NAb analysis set. Subjects will be analyzed according to the treatment actually received.

### **11.4. Statistical Methods**

For continuous variables, descriptive statistics will include the following information: the number of subjects reflected in the calculation (n), mean, standard deviation, Q1, median, Q3, minimum, and maximum. For categorical or ordinal data, frequencies and percentages will be displayed for each category.

Baseline is defined as the last assessment obtained before the first dose of study drug unless specified otherwise.

Statistical analyses will be conducted separately in each cohort. For the purpose of the study analysis, cohorts A, A1, B, and B1 are independent with separate type I error control for each cohort.

#### 11.4.1. Subject Disposition

The following will be provided:

- The total number of screened subjects, defined as signed the ICF
- The total number of randomized subjects: received a randomization number
- The total number of subjects randomized but not receiving study treatment
- The total number of subjects who discontinued the study, and the reasons for discontinuation
- A listing of subjects treated but not randomized, subjects randomized but not treated, and subjects randomized but not treated as randomized
- A listing of subjects prematurely discontinued from the study, along with reasons for discontinuation

#### 11.4.2. Demography and Baseline Characteristics

Demographic and baseline characteristics will be summarized descriptively by treatment group, and by all subjects combined.

#### 11.4.3. Efficacy Analyses

##### 11.4.3.1. Primary Efficacy Analysis

###### Cohort A

The cohort A primary efficacy endpoint described in Section 4.1.1 will be analyzed in the seronegative mFAS-A population (Section 11.3.1). All post-baseline efficacy assessments obtained up to last scheduled visit (day 29) in EAP will be included for the primary analysis.

In order to account for the correlation among subjects within a household and control the associated type 1 error inflation, a generalized linear model will be used to estimate the odds ratio between the treatment groups by using the GEE approach. This model estimates a single within-household correlation coefficient. The model will include the fixed category effects of treatment group (placebo versus REGN10933+REGN10987), region (US versus ex-US), and age ( $\geq 12$  to  $< 50$ ,  $\geq 50$  years). The model will use a compound symmetry covariance matrix and estimate the odds ratio between the treatment groups and corresponding 95% CI and p-value.

If the GEE model fails to converge due to most households containing only a single study subject in seronegative mFAS-A or the percentage of households in cohort A with only a single study subject is 70% or more, then a logistic regression model will be used, with treatment, region, and age group as fixed effects. The threshold of 70% was based on simulations of within-household

correlation which show the type I error rate is inflated and the power is decreased when the proportion of single-subject households is high. Additional details will be provided in the SAP. If the logistic regression model does not converge, an exact logistic regression will be used. The estimates of odds ratio, the corresponding 95% CI and p-value will be provided from logistic regression (or exact logistic regression) for comparison of REGN10933+REGN10987 against placebo group.

In cohort A, a subject will be considered having a symptomatic RT-qPCR confirmed SARS-CoV-2 infection (broad-term) during the EAP if any of the post-baseline RT-qPCR results during EAP are positive with at least 1 symptom within 14 days of a positive RT-qPCR result.

### **Cohort B**

The cohort B primary efficacy endpoint described in Section 4.2.1 will be analyzed in the seronegative mFAS-B population (Section 11.3.1). The same statistical methods as described for cohort A will be used to obtain the estimate of odds ratio and p-value for comparison between the treatment groups.

In cohort B, a subject will be considered having a symptomatic RT-qPCR confirmed SARS-CoV-2 infection (broad-term) during the EAP if subjects have at least 1 symptom within 14 days of a positive RT-qPCR result at baseline or during the EAP.

### **Handling of Missing Central Lab SAR-CoV-2 RT-qPCR Data for Both Cohort A and Cohort B**

Subjects with COVID-19 symptoms that are missing a central lab-determined RT-qPCR test during the EAP (eg, are too sick to go to the study site) but have a positive SARS-CoV-2 test from a local lab (eg, in the hospital) will be considered as having a symptomatic infection if any of the symptoms occurred within 14 days of the positive SARS-CoV-2 test(s).

The graphical display using Kaplan-Meier curve for the time to first symptom will also be provided.

#### **11.4.3.1.1. Sensitivity Analyses**

Robustness of the primary analyses results in cohort A and cohort B will be assessed through sensitivity analyses as follows:

##### **Sensitivity analysis by excluding subjects who develop asymptomatic or symptomatic SARS-CoV-2 infection within 72 hours of the study drug administration**

This analysis assesses for the sensitivity of the results to subjects who may have had undetected infections prior to dosing. That is, a subject had any onset of a positive RT-qPCR within 72 hours of the study drug administration will be excluded for this sensitivity analysis.

This sensitivity analysis will only be performed for cohort A primary endpoint.

##### **Sensitivity analysis by excluding subjects from non-good clinical practice (GCP) Compliant Site(s)**

To access the impact of sites that had non-GCP compliance issues on the primary efficacy points, the primary analyses will be performed by excluding non-GCP compliant site(s).

This sensitivity analysis will be performed for both cohort A and cohort B primary endpoints.

#### 11.4.3.1.2. Subgroup Analyses

To assess the homogeneity of the treatment effect across various subgroups, the primary analysis model with GEE approach will be applied to each subgroup if applicable; otherwise, the logistic regression model will be used. Odds ratio between the treatment groups and corresponding 95% CI will be provided, as well as the within-household correlation coefficient from GEE approach, within each subgroup.

The subgroups of interest to be evaluated for cohort A primary endpoint include, but are not limited to:

- Stratification age group (years) ( $\geq 12$  to  $< 18$ ,  $\geq 18$  to  $< 50$ ,  $\geq 50$ ) and the additional age group:  $\geq 12$  to  $< 18$ ,  $\geq 18$  years
- Sex
- Race
- Ethnicity
- BMI ( $< 30$ ,  $\geq 30$ )
- Number of study subjects in cohort B within a household (0,  $\geq 1$ ) (cohort A only)
- Total household size including the household member(s) not participating this study (2, and  $> 2$ )
- Region (US, ex-US)

Additional subgroup analyses will be defined in the SAP.

#### 11.4.3.2. Key Secondary Efficacy Analyses

For cohort A, the key binary endpoint of the proportion of subjects who have a RT-qPCR confirmed SARS-CoV-2 infection (regardless of symptoms) during the EAP, the same statistical method used in the primary analysis will be applied. If a subject's overall infection status during the EAP cannot be determined due to missing RT-qPCR results, the following rules will be applied to impute the missing RT-qPCR data.

1. For subjects satisfying the criteria specified in the handling of missing central lab SARS-CoV-2 RT-qPCR data of the analysis of primary efficacy variables, the corresponding visit(s) will be considered as having a positive RT-qPCR test.
2. After the first step above, each planned visit with missing RT-qPCR data will be imputed 100 times to generate 100 complete datasets based on the predicted probability using the fully conditional specification (FCS) ([Van Buuren, 2006](#)) through the logistic regression. The logistic regression model includes the fixed effect factors of treatment group, region, age group, and RT-qPCR testing status at other analysis visits during the EAP. This imputation will repeat by iterating for each analysis visit with missing RT-qPCR testing status. Full details on details on the use of FCS from the SAS MI procedure will be provided in the SAP.

For the key binary endpoint of the proportion of subjects with viral load  $>4$  (log10 copies/mL), if NP swab viral load data is missing for a visit, it will not be imputed regardless of symptoms. Only non-missing available NP swab viral load data will be used for the analysis of this endpoint. Only subjects with at least one post-baseline viral load (log10 copies/mL) data in NP swab samples will be included in the analysis.

For cohort A the key binary endpoint regarding the index case linkage to R10933-10987-COV-2067, the Fisher's exact test will be used.

For continuous key secondary endpoints in cohort A and cohort B (eg, number of weeks of high viral load  $>4$  (log10 copies/mL) in NP swab samples and number of weeks of symptomatic RT-qPCR-confirmed SARS-CoV-2 infection (broad-term) during the EAP, etc), visits with missing viral load regardless of symptoms and visits with missing RT-qPCR that do not have any broad-term symptoms within 14 days will not be considered as meeting these endpoint criteria, respectively. These endpoints will be analyzed by the non-parametric method, a stratified Wilcoxon rank sum test (Van Elteren Test) with the region and age group. Descriptive statistics will be provided for number (%) of subjects with each interval of duration in weeks (ie, 0 week,  $>0$  to  $\leq 1$  week,  $>1$  to  $\leq 2$  weeks, etc) within each treatment group. The total weeks of infection and normalized duration (eg, average duration infection per 1000 subjects) per treatment group will also be reported.

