### **8.4. Method of Treatment Assignment**

Subjects will be randomized in a 1:1 ratio to receive REGN10987+REGN10933 or placebo according to a central randomization scheme provided by an interactive web response system (IWRS) to the designated study pharmacist (or qualified designee). Randomization will be performed by individual study subjects, not by households. In addition to a randomization number, all subjects randomized will be given a household identification number in the case that multiple members of the same household are enrolled and receive study drug. This ensures that any correlation among subjects within the same household may be considered in the statistical analysis. The REGN10987 and REGN10933 dose for adult, adolescent, and pediatric subjects is described in Section 8.1.

Randomization will be performed by site and stratified as follows:

- Local diagnostic assay for SARS-CoV-2 from appropriate samples (positive, negative, or undetermined)
- Age and/or weight:
  - <12 years and <10 kg,
  - <12 years and  $\geq$ 10 kg to <20 kg,
  - <12 years and  $\geq$ 20 kg
  - $\geq$ 12 years and <18 years
  - $\geq$ 18 years and <50 years
  - $\geq$ 50 years

Note that the cohorts used in the analysis are defined by the baseline central lab SARS-CoV-2 RT-qPCR results, not by the local diagnostic assay.

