#### Seronegative mFAS-B Subjects

The overall type I error will be controlled for the primary hypothesis in cohort B based on a 2-sided test at an alpha level of 0.05 as follows.

H0: There is no treatment difference between REGN10933+REGN10987 and placebo in proportion of subjects who subsequently develop signs and symptoms (broad-term) within 14 days of a positive RT-qPCR at baseline or during the EAP

H1: There is a treatment difference between REGN10933+REGN10987 and placebo in the proportion of subjects who subsequently develop signs and symptoms (broad-term) within 14 days of a positive RT-qPCR at baseline or during the EAP

If statistical significance is established for the primary efficacy endpoint in cohort B, a hierarchical testing procedure will be applied to the key secondary endpoints in cohort B at a 2-sided 0.05 significance level. The order of testing sequence for key secondary endpoints is presented in [Table 11](#).

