The following general rules will be used for efficacy variables and all SARS-CoV-2 RT-qPCR test results are based on the central lab testing:

- For cohort determination, qualitative PCR results from swabs taken prior to or within 2 hours of study drug administration will be used if there are no available test results prior to study drug administration.
- Quantitative values of viral load will be determined based on NP swabs only. For baseline viral load, only RT-qPCR results from swabs taken prior to dosing will be used.
- A positive infection will be defined based on any available RT-qPCR result (either NP, nasal or saliva) which is reported as “detected”. A negative infection will be defined based on all available RT-qPCR results (either NP, nasal or saliva) which are reported as “not detected”.
- Symptomatic SARS-CoV-2 infection (broad-term) is defined as a positive central lab SARS-CoV-2 RT-qPCR result (either NP, nasal or saliva) associated with signs and symptoms with the onset date occurring within 14 days of a positive RT-qPCR during the EAP.
- For subjects in Cohort B, symptomatic SARS-CoV-2 infection (broad-term) is defined as having at least one signs and symptoms with the onset date occurring within 14 days of a positive RT-qPCR (either NP, nasal or saliva) at baseline or during the EAP.

- Viral loads less than the lower limit of quantification of the PCR assay but with positive qualitative results will be set to half of the lower limit of quantification of the PCR assay; values with nondetectable RNA will be set to 0 log₁₀ copies/mL. Viral load values above the upper limit of quantification will be re-tested using the reflex test and the corresponding quantitative value will be used in the analysis.

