4.5.6. Cohort B Key Secondary Efficacy Variables

The key secondary efficacy variables listed below are continuous (C) variables.

Key Secondary Efficacy Variables	Type
Number of weeks of symptomatic SARS-CoV-2 infection (broad-term) within 14 days of a positive RT-qPCR at baseline or during the EAP	C
Number of weeks of high viral load >4 (log10 copies/mL) in NP swab samples during the EAP	C

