5.7.1.2. Subgroup Analyses

To assess the homogeneity of the treatment effect across various subgroups, the primary analysis model with GEE approach will be applied to each subgroup if applicable; otherwise, the logistic regression model will be used. Odds ratio between the treatment groups and corresponding 95% CI will be provided, as well as the within-household correlation coefficient from GEE approach, within each subgroup.

The following subgroups of interest for Cohort A and Cohort B primary endpoints will be evaluated:

- Stratification age (years) group (≥ 12 to < 18 , ≥ 18 to < 50 , ≥ 50), and the additional age group: ≥ 12 to < 18 , and ≥ 18 years
- Sex
- Race (American Indian or Alaskan Native, Asian, Black or African American, Native Hawaiian or Other Pacific Islander, White and Other, where “Other” may include, for example, not reported, unknown, and multiracial, etc.) and an additional race group (White Hispanic or Latino, White not Hispanic or Latino, Black Hispanic or Latino, Back not Hispanic or Latino, and Other)
- Ethnicity (Hispanic or Latino, not Hispanic or Latino, and not reported or unknown)
- BMI (< 30 , ≥ 30)
- Number of study subjects in cohort B within a household (0, ≥ 1) (Cohort A only)
- Total household size including the household member(s) not participating this study (2, and > 2)
- Region (US, ex-US)
- Baseline high risk factor (Yes versus No) (as defined in Section 4.1)
- Healthcare worker (Yes/No) per exposure risk factor eCRF
- High viral load ($> 4 \log 10$ copies/ml) at baseline (Yes/No) (Cohort B only)

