The secondary and exploratory continuous efficacy endpoints such as TWA, AUC, and maximum viral load (\log_{10} copies/mL) will be analyzed using the ANOVA including treatment group, region, and age group as fixed effects in the model. The continuous endpoints regarding change from baseline in cohort B (e.g., TWA of change/percent change from baseline) will be analyzed using the ANCOVA model with treatment group, region, and age group as fixed effects, and the relevant baseline values as covariate as well as treatment-by-covariate interaction. The REGN10933+REGN10987 group will be compared to the placebo group and corresponding least square of mean difference, standard error (SE) and 95% confidence interval will be provided. For

other endpoints with non-normal/skewed distribution (e.g. number of days of symptoms (strict-term, and CDC definition, etc.)), Van Elteren test will be used.

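### Cohort B's test of weeks of high viral load takes no account of baseline viral load, which the trial measures; the test is valid but may give up power

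*Protocol*

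**What the plan says.** The endpoint is "Number of weeks of high viral load >4 (log10 copies/mL) in NP swab samples during the EAP" (SAP 4.5.6). It is the second of two cohort B key secondaries (Protocol Table 11, SAP Table 3). If the cohort B primary succeeds, "a hierarchical testing procedure will be applied to the key secondary endpoints in cohort B at a 2-sided 0.05 significance level" (Protocol 11.4.4).

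Protocol 11.4.3.2 gives one method for the continuous key secondaries of cohorts A and B together: "a stratified Wilcoxon rank sum test (Van Elteren Test) with the region and age group". SAP 5.7.3 repeats it. Cohort A is PCR-negative at entry, so baseline load carries no useful information there. Cohort B is PCR-positive by definition.

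Elsewhere the plan treats baseline load as relevant in cohort B:

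- It is a listed baseline characteristic (SAP 4.1).
- It has its own rule: "For baseline viral load, only RT-qPCR results from swabs taken prior to dosing will be used" (SAP 4.5).
- High viral load "at baseline (Yes/No) (Cohort B only") is a subgroup factor for the cohort B primary endpoint, at the same cut of 4 log10 that defines this endpoint (SAP 5.7.1.2).
- The change-from-baseline endpoints, which are not key secondaries, are analysed by ANCOVA with "the relevant baseline values as covariate as well as treatment-by-covariate interaction" (SAP 5.7.4).

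Baseline load is not a randomization stratum. Protocol 8.4 stratifies by site, local assay result (positive, negative or undetermined) and age or weight.

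**The concern.** The 96-hour limit in inclusion criterion 2 runs from the index case's sample, not from the subject's own infection. PCR-positive contacts therefore enter at varying intervals after infection. Someone who enters at or below 4 log10 and stays there contributes zero weeks in either arm. Someone who enters well above 4 contributes weeks almost regardless of treatment. If baseline load predicts later load, that difference between subjects stays in the ranks as noise, because the strata are only region and age group.

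At stake is the power of the alpha-controlled test behind the cohort B objective on duration of high-viral-load infection. A chance difference between arms in baseline load would also go uncorrected.

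**Working it through.** **Inputs from the documents.** 200 seronegative cohort B subjects, 50% placebo symptom rate, relative risk 0.5, 2-sided alpha 0.05 (Protocol 11.2.2), and 1:1 allocation (Protocol 8.4), hence 100 per arm. No power, effect size or distribution is given for weeks of high viral load.

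**1. The plan's own cohort B figure (primary endpoint).** For 50% versus 25%, the normal approximation is

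power = Φ{[0.25·√100 − 1.96·√(2·0.375·0.625)] / √(0.5·0.5 + 0.25·0.75)} = Φ{(2.5 − 1.342)/0.661} = Φ(1.75) = 96.0%.

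Exact power of the 2-sided Fisher test is 94.5%. The stated power above 90% reproduces. It says nothing about the endpoint at issue.

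**2. Analytic guide.** Full adjustment for a covariate with rank correlation ρ to the outcome multiplies residual variance by 1 − ρ². A test planned at 80% power then has power Φ{(1.960 + 0.842)/√(1 − ρ²) − 1.960}:

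- ρ = 0.2: 81.6%
- ρ = 0.3: 83.6%
- ρ = 0.5: 89.9%
- ρ = 0.7: 97.5%

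These are upper guides for a yes/no stratum, which uses only part of the information in a continuous baseline.

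**3. Simulation of the proposed test.** The Van Elteren statistic sums (rank sum − expectation)/(n+1) over strata, with tie-corrected variance. It was run with region and age strata, with and without a further stratum for baseline above 4. All viral-load inputs are assumptions.

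| Assumed inputs | Rank correlation, baseline to weeks | Planned test | With baseline stratum |
|---|---|---|---|
| Weak link (three scenarios) | about 0.15 | 89%, 90%, 93% | 89%, 91%, 92% |
| 84% enter above 4 | 0.33 | 79% | 79% |
| 75% enter above 4 | 0.51 | 79% | 87% |
| 69% enter above 4 | 0.62 | 69% | 80% |
| Strong link, 80% above 4 | about 0.57 | 85% | 96% |
| Strong link, 60% above 4 | about 0.70 | 64% | 91% |
| Strong link, 40% above 4 | about 0.73 | 50% | 84% |

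The strong-link rows assume these percentages of subjects with 0, 1, 2, 3 and 4 weeks:

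- Baseline above 4: placebo 5/35/35/15/10, active 15/50/25/7/3.
- Baseline at or below 4: placebo 80/12/5/2/1, active 90/7/2/1/0.

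Compare within rows only, because the assumed treatment effect differs between the sets. With no treatment effect, rejection stayed near 5% for both tests.

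**4. Chance imbalance.** The standard deviation of the between-arm difference in the share above 4 is √[2p(1 − p)/100]. This is 7.1 percentage points at p = 0.50 and 5.2 at p = 0.84.

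**5. Subjects with no pre-dose value.** In the strong-link row with 60% above 4, placing 10% of subjects in the lower category for want of a value reduces power with the stratum from about 91% to about 87%. The planned test has 64% there.

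**The case against.** Four stronger readings are tempting, and the documents do not support them.

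- **Cohort B includes infection at any stage, much of it already clearing.** This overlooks the analysis set. Seronegative mFAS-B requires negative results on all available assays of three, including anti-S IgA, and no symptoms at baseline (SAP 3.1). Known prior positives are excluded, as is a respiratory illness suggestive of COVID-19 in the previous six months (Protocol 7.2.2). What stands is narrower: no criterion limits time since the subject's own infection, and the plan's own yes/no subgroup presumes values on both sides of 4.
- **The planned test is biased, or an imbalance invalidates it.** It is not. Under individual randomization, chance imbalance is already reflected in the test's null distribution. Any imbalance will also be visible, because baseline load is summarised by arm (SAP 4.1 and 5.1).
- **The gain is large.** That holds only under a strong link. Among antibody-negative contacts a low value may be early and rising rather than late and falling, which would weaken the link. The strong-link rows give 80% of low-baseline placebo subjects no weeks at all, and that assumption drives their result. In the weak-link rows the stratum gains nothing.
- **The cohort B primary model should also adjust for baseline load.** Nothing here was calculated for that endpoint. In a logistic model the adjustment would change the odds ratio to one conditional on baseline load. It would also drop subjects without a pre-dose value, since SAP 4.5 can assign cohort from a swab taken up to 2 hours after dosing.

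Against this, baseline and outcome share one assay and one threshold, so some link is likely, and the extra stratum cost no material power in any scenario run.

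**Conclusion.** The point holds as a question of efficiency, and it is minor. The alpha-controlled cohort B test of weeks of high viral load leaves out a likely prognostic baseline value that the plan measures, defines and adjusts for in lower-ranked endpoints. The planned test is valid and keeps its type I error.

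The possible gain runs from none, through 79% to 87%, to about 50% to 84%, at rank correlations of about 0.15 to 0.3, 0.5 and 0.7. It rests on 100 subjects per arm and on viral-load distributions that the documents do not supply. It matters only if testing reaches this second key secondary. The documents also do not say whether the day 1 swab can count as a week of high viral load. If it can, baseline load enters the outcome directly and the adjustment matters more.

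**What to change.** Before unblinding, amend Protocol 11.4.3.2 and SAP 5.7.3 for this cohort B endpoint only. Add baseline viral load (at or below 4, above 4 log10 copies/mL) as a Van Elteren stratum alongside region and age group. Specify with it:

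- a collapse rule: drop age first if any stratum contains only one arm;
- a rule for subjects with no pre-dose NP value. If they go into the lower category, say so and accept the cost shown in step 5.

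The change is a few sentences and one variable already in the dataset. SAP section 1 allows revision on blinded review before the first-step lock. The downside is up to 2 × 2 × 2 = 8 strata in about 200 subjects (with age in the two groups of the primary model), some of them small. If the sponsor prefers to leave the confirmatory test alone, the same stratified test as a pre-specified sensitivity analysis would show whether baseline imbalance drives the result, but would not recover power.
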